### **10.3.2.3 Absolute Change from Baseline in Weight, Weight-for-Age Z-score**

The calculation of weight z-score is similar to that of BMI z-score (using the CDC growth charts and the derivation described above). Using the same equation above,  $X$  in the equation is the collected weight and  $L$ ,  $M$ , and  $S$  parameters are selected from the CDC weight-for-age chart. The WTAGE file contains these parameters by sex and age; it is available at the website [http://www.cdc.gov/growthcharts/percentile\\_data\\_files.htm](http://www.cdc.gov/growthcharts/percentile_data_files.htm).

NOTE: The CDC growth charts are designed for use in pediatric populations (2 to 20 years of age).

Weight and weight-for-age z-score will be analyzed in a similar way to BMI and BMI-for-age z-score.

### **10.3.2.4 Absolute Change from Baseline in stature and stature-for-age z-score**

The calculation of stature z-score is similar to that of BMI z-score (using the CDC growth charts and the derivation described above). Using the same equation above,  $X$  in the equation is the collected stature and  $L$ ,  $M$ , and  $S$  parameters are selected from the CDC stature -for-age chart. The STAGE file contains these parameters by sex and age; it is available at the website [http://www.cdc.gov/growthcharts/percentile\\_data\\_files.htm](http://www.cdc.gov/growthcharts/percentile_data_files.htm).

NOTE: The CDC growth charts are designed for use in pediatric populations (2 to 20 years of age).

Stature and stature-for-age z-score will be analyzed in a similar way to BMI and BMI-for-age z-score.

### **10.3.2.5 Absolute change from Baseline in LCI2.5 and LCI5.0**

The LCI assessment at scheduled visits will be performed in multiple replicates. The LCI values at each visit included in the analysis will be the value calculated from the technically acceptable washout replicates.

When there is only one LCI value considered acceptable by the LCI central reader, the value will NOT be used. The assessment for that subject at the corresponding visit will not be included in the analysis; when there are at least 2 LCI values considered acceptable by the LCI central reader, the arithmetic mean of the values from the accepted trials will be calculated as the value at the corresponding visit.

LCI2.5 and LCI5.0 will be analyzed in a similar way to BMI and BMI-for-age z-score.

### **10.3.2.6 Analysis of Pulmonary Exacerbation-related Other Secondary Pharmacodynamic Variables**

**Time-to-first pulmonary exacerbation:** Time-to-first pulmonary exacerbation, defined as days from study drug initiation in the Study 115B to first pulmonary exacerbation, will be analyzed using Kaplan-Meier (KM) method based on the FAS for the Cumulative Study Period. Cumulative incidence of pulmonary exacerbation will be summarized for the overall group. Subjects without an exacerbation will be considered censored at the end date of the Cumulative Study Period.

**Number of pulmonary exacerbations:** The number of pulmonary exacerbations starting during the Cumulative Study Period (including both on-treatment events and events after treatment discontinuation), normalized by the time spent in the Cumulative Study Period (last date in the Cumulative Study Period – first date in the Cumulative Study Period + 1), will be summarized for the overall group based on the FAS.

**Number of CF-related hospitalizations through last visit:** The number of CF-related hospitalizations occurring during the Cumulative Study Period (including both on-treatment events and events after treatment discontinuation), normalized by the time spent in the Cumulative Study Period (last date in the Cumulative Study Period – first date in the Cumulative Study Period + 1), will be summarized for the overall group based on the FAS.

### **10.3.2.7 Absolute Change in FE-1 Levels From Baseline**

The raw values and absolute change from parent study baseline in FE-1 will be summarized at each scheduled visit during the Current Study Period for the overall group based on the 116 FAS. In addition, the number and percentage of subjects with shift changes from parent study baseline [ $<15 \mu\text{g/g}$ ,  $\geq 15 \mu\text{g/g}$  to  $<200 \mu\text{g/g}$  (consistent with pancreatic insufficient), and  $\geq 200 \mu\text{g/g}$  (consistent with pancreatic sufficient)] at each visit and at any visits ( $<15 \mu\text{g/g}$ ,  $\geq 15 \mu\text{g/g}$  to  $<200 \mu\text{g/g}$ , and  $\geq 200 \mu\text{g/g}$ ) in the Current Study Period will be provided. A spaghetti plot of the FE-1 values will also be provided including Study 115B baseline, and visits in the Current Study Period.

### **10.3.2.8 Absolute Change in Serum Levels of IRT From Baseline**

The raw values and absolute change from parent study baseline in IRT will be summarized at each scheduled visit during the Current Study Period for the overall group based on the 116 FAS. A spaghetti plot of the IRT values will also be provided including Study 115B baseline, and visits in the Current Study Period.

### **10.3.2.9 Analysis in Microbiology Cultures**

The presence of bacteria will be descriptively summarized by subjects' counts and percentages. Number and percentage of subjects with microbiology cultures in each category during the Current Study Period will be summarized descriptively by visit based on the 116 FAS, for each possibly-detected organism.

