Microbiology: Microbiological endpoints, such as bacterial colony counts and selection of resistant bacterial strains, are well-established endpoints used to evaluate antimicrobial therapies in CF. Because compounds, such as IVA, that restore CFTR function may increase hydration of airway secretions and lead to a decrease in acquisition of bacteria in the CF airway, acquisition of bacteria is included as another secondary endpoint in this study. Because the majority of subjects in this study will not expectorate spontaneously, oropharyngeal swabs will be used to obtain airway cultures.

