## 12.3.3.2.5 Change in Microbiology from Baseline

Raw values and absolute change from Cumulative Study Baseline in microbiology at each visit in the Cumulative Study Period will be summarized descriptively based on FAS, similar to sweat chloride. Percentage of subjects with cultures positive at each visit in the Cumulative Study Period will be summarized descriptively based on the FAS for each possibly-detected organism.

Additional analysis may be added in the SAP, if any.

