### **6.2 Secondary Endpoints**

The following endpoints will be analyzed using baseline values in the previous (parent) study (i.e., Study 115 Part B [Study 115B]):

- Absolute change from baseline in sweat chloride

- Absolute change from baseline in body mass index (BMI) and BMI-for-age z-score
- Absolute change from baseline in weight and weight-for-age z-score
- Absolute change from baseline in stature and stature-for-age z-score
- Time-to-first pulmonary exacerbation from baseline
- Number of pulmonary exacerbations from baseline
- Number of CF-related hospitalizations from baseline
- Absolute change from baseline in fecal elastase-1 (FE-1) levels
- Absolute change from baseline in serum levels of immunoreactive trypsinogen (IRT)
- Change from baseline in microbiology cultures
- Absolute change from baseline in lung clearance index LCI2.5
- Absolute change from baseline in LCI5.0

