## 9 ANALYSIS PERIODS

### 9.1 Current Study Period

The **Current Study Period** starts from the first dose date of study drug in Study 116 to the last day in Study 116.

The **Treatment-Emergent Period for the Current Study Period** starts on or after the first dose date of study drug in Study 116 to 14 days (inclusive) after the last dose of study drug in Study 116 or up to the last day in Study 116, whichever occurs first.

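### The secondary endpoint is change from baseline in microbiology cultures, but SAP 10.3.2.9 summarises only Study 116 visits, so bacterial acquisition cannot be concluded from the planned output

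*SAP*

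**What the plan says.** SAP 6.2 introduces its list of secondary endpoints with "The following endpoints will be analyzed using baseline values in the previous (parent) study", that is, Study 115B. The list includes "Change from baseline in microbiology cultures", and Protocol 7.2 has the same entry. Protocol 9.3.3 gives the reason for taking cultures: restoring CFTR function may reduce bacterial colonisation of the airway, and so "acquisition of bacteria is included as another secondary endpoint in this study".

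Protocol 12.3.3.2.5 planned two summaries. The first, on the FAS, covered observed results and their change from the Study 115B baseline at every visit of both studies. The second was by organism: "Percentage of subjects with cultures positive at each visit in the Cumulative Study Period will be summarized descriptively based on the FAS".

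SAP 10.3.2.9 keeps only a tabulation at each visit: "Number and percentage of subjects with microbiology cultures in each category during the Current Study Period will be summarized descriptively by visit". It is done separately for each organism, on the 116 FAS. SAP 9.1 defines the period used as one that "starts from the first dose date of study drug in Study 116 to the last day in Study 116". The categories are not defined.

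**The concern.** Acquisition is a change within a child, from culture-negative at baseline to culture-positive later. Clearance is the reverse. Both need the baseline and later results of the same child. SAP 10.3.2.9 reports each Study 116 visit on its own, and the Study 115B baseline falls outside the period it covers. A stated secondary endpoint therefore has no analysis that answers it. A stable percentage positive could be read as no acquisition when it may hide equal numbers of children gaining and losing an organism.

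**Working it through.** **Comparison of the sections**

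- Endpoint (SAP 6.2, Protocol 7.2): change from the Study 115B baseline.
- Scientific question (Protocol 9.3.3): acquisition.
- Protocol analysis (12.3.3.2.5): change from the Study 115B baseline, plus percentage positive by visit across both studies.
- SAP analysis (10.3.2.9): percentage in each category by visit, Study 116 only.
- Neighbouring SAP sections: sweat chloride (10.3.2.1), BMI (10.3.2.2) and IRT (10.3.2.8) all specify change from the parent-study baseline. Weight, stature and LCI (10.3.2.3 to 10.3.2.5) follow BMI by reference. FE-1 (10.3.2.7) also plans "the number and percentage of subjects with shift changes from parent study baseline", which is the format a categorical culture result needs.

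Microbiology is the only change-from-baseline endpoint in SAP 6.2 whose analysis section omits the baseline. The available text gives no reason.

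**The plan's own figure**

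SAP 7.2 expects 50 subjects: 56 × (1 − 0.10) = 50.4, about 50. This is reproduced and used as n below.

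**What visit counts can tell us about acquisition**

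Let b be the number positive at baseline, v the number positive at a visit, and a the number newly positive. Assume all n subjects have both results. Then:

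- a is at least max(0, v − b)
- a is at most min(v, n − b)
- the number cleared is a + b − v

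If b is not reported, a can be anything from 0 to v, and the denominator n − b is unknown as well. The documents give no culture prevalence, so the counts below are assumptions, with n = 50.

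| Positive at baseline (b) | Positive at visit (v) | New acquisitions (a) | Baseline-negative (n − b) | Proportion acquiring |
|---|---|---|---|---|
| not shown | 10 | 0 to 10 | not shown | not determinable |
| 10 | 10 | 0 to 10 | 40 | 0% to 25% |
| 15 | 15 | 0 to 15 | 35 | 0% to 42.9% |
| 10 | 15 | 5 to 15 | 40 | 12.5% to 37.5% |
| 25 | 20 | 0 to 20 | 25 | 0% to 80% |

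The first row is what SAP 10.3.2.9 would produce. The other rows give the reader a baseline percentage that the SAP does not plan to show, and the range stays wide. In the second row, 10/50 positive at both times fits both no change in any child and 10 children acquiring while 10 others clear (10/40 = 25%). Only the paired table gives a single value.

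**The case against.** The strongest reply is that the listed endpoint is change from baseline, and acquisition appears only in the rationale. A comparison of baseline and visit prevalence would be one fair reading of change, and the protocol's own analysis section specified no shift table or acquisition rate. This stands in part: a paired table goes further than the protocol text. But Protocol 9.3.3 itself calls acquisition a secondary endpoint, and SAP 10.3.2.9 does not provide the prevalence comparison either. Restoring the protocol wording would not be enough, because an absolute change is not defined for a qualitative culture.

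Other replies have less force:

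- SAP 10.1 promises individual listings. If these include Study 115B cultures, conversions could be counted by hand. The SAP does not say that they do, and such a count would be post hoc.
- A culture is scheduled on Study 116 Day 1. It comes after the Study 115B treatment period, whereas SAP 10.1 sets baseline before the first Study 115B dose.
- The statement in SAP 6.2 about parent-study baselines shows the intention, but 10.3.2.9 does not carry it out.
- Parts of the SAP are redacted, including an entry after 10.3.2.9 in the contents list. Its content is unknown, and it does not supply a baseline comparison in the section assigned to this endpoint.
- The study is an uncontrolled, descriptive safety rollover, and no primary conclusion depends on cultures. That limits the consequence. The remedy is equally descriptive.

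**Conclusion.** The concern holds. Followed as written, SAP 10.3.2.9 leaves a stated secondary endpoint without a matching summary and drops the baseline comparison that Protocol 12.3.3.2.5 had planned. In the illustration, 10/50 positive at a visit is compatible with anything from 0 to 10 acquisitions; adding an unpaired 20% baseline still leaves 0% to 25% of the 40 baseline-negative children.

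The conclusion about the missing comparison follows from the text and does not depend on these counts, which are assumed apart from n = 50. Describing the SAP output as percentage positive is a paraphrase of its undefined categories. That Study 115B baseline cultures are available is implied by SAP 6.2 and Protocol 12.3.3.2.5, but the Study 115B culture schedule is not in the documents. The change should be made before database lock, although the primary safety objective does not depend on it.

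**What to change.** Revise SAP 10.3.2.9 to add, for each organism on the 116 FAS:

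1. A 2×2 shift table (negative or positive) from the Study 115B baseline to each of Weeks 24, 48, 72 and 96, with the number of subjects who have both results.
2. The number and percentage newly positive at any Study 116 visit among subjects negative at the Study 115B baseline, with an exact 95% CI.
3. The number and percentage culture-negative at the last visit among subjects positive at baseline, with an exact 95% CI.

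In the same revision, define the culture categories and state how missing baseline cultures are handled. Add a microbiology row to the visit windows in SAP Appendix C, which has none, and say how early-termination cultures are assigned.

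The cost is SAP wording and one table per organism, modelled on the FE-1 shift table. Study 116 cultures are already scheduled, so no new collection is needed. The programming must bring in the Study 115B baseline cultures, as it must already bring in Study 115B baselines for the other endpoints.

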## **10.4 Efficacy Analysis**

Not Applicable.

## **10.5 Safety Analysis**

### **Observational Cohort**

Listings of SAEs will be provided based on all subjects enrolled in the Observational Cohort.

### **Treatment Cohort**

Evaluating safety of long-term LUM/IVA treatment in the Treatment Cohort is the primary objective of this study. The overall safety profile of study drug will be assessed in terms of the following safety and tolerability endpoints:

- Treatment-emergent adverse events (TEAEs)
- Clinical laboratory values (serum chemistry, hematology, coagulation studies and urinalysis)
- ECGs (standard 12-lead)
- Vital signs
- Pulse oximetry
- OEs
- Spirometry (subjects  $\geq 3$  years age at screening in Study 115B)

The safety analysis will be performed based on the 116 Safety Set for the Current Study Period. Only descriptive summary statistics of safety data will be provided (i.e., no statistical hypothesis testing will be performed). All listings will be provided based on the 116 All Subjects Set.

The safety summaries described in the sections below will be performed for the Treatment Cohort based on the Current Study Period only.

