#### **Safety Analysis**

All treatment-emergent AE (TEAE) summaries will be described using the incidence of TEAEs and number of events per 100 patient-years (number of events adjusted for the total duration of exposure) for the Cumulative Study Period.

Continuous safety endpoints will be summarized descriptively at each visit during the Cumulative Study Period.

For the categorical laboratory, vital, and ECG variables, the number and percentage of subjects in each category during the Treatment-emergent Period of the Cumulative Study Period will be summarized.

The safety analysis for the Cumulative Study Period will be based on the Safety Set, which will include all subjects who received at least 1 dose of study drug in Study 115B.

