### **Safety Sets**

**Safety Set:** The Safety Set will include all subjects who received at least 1 dose of study drug in Study 115B.

**116 Safety Set:** The 116 Safety Set will include all subjects dosed in Study 115B who are exposed to any amount of study drug in the Study 116 Treatment Cohort.

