### Treatment-emergent Period for the Cumulative Study Period

The Treatment-emergent Period for the Cumulative Study Period is the period on or after the first dose of study drug in the previous study to 14 days (inclusive) after the last dose of study drug in Study 116 or up to the last day in Study 116, whichever occurs first. For subjects not enrolled in Study 116, the Treatment-emergent Period for the Cumulative Study Period will be

the period on or after the first dose of study drug in the previous study to 14 days (inclusive) after the last dose of the previous study, or last date of the previous study, whichever occurs first.

Other specific periods may be defined in the SAP and used for any targeted analysis as deemed necessary.

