## 12.3.2.4 Study Drug Exposure and Compliance

#### **Study Drug Exposure**

Duration of study drug exposure is defined as follows: last dose date of the Cumulative Study Period – first dose date of the Cumulative Study Period + 1 day, regardless of any dose interruptions.

Duration of study drug exposure as well as number of sticks administered defined as (total number of sticks dispensed) – (total number of sticks returned) will be summarized descriptively overall based on Safety Set for the Cumulative Study Period. Additionally, the total duration of treatment exposure, defined as the sum of the subject's duration of treatment exposure and expressed in subject-years, will be provided. Duration of exposure will also be summarized as a categorical variable.

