#### 12.3.4.1 Adverse Events

For analysis purposes, AEs will be classified as pretreatment AEs, TEAEs, or post-treatment AEs.

- Pretreatment AEs: AEs occurred before initial dosing of study drug in the previous study.
- **TEAE:** any AE that increased in severity or that was newly developed during the Treatment-emergent Period of the Cumulative Study Period.
- **Post-treatment TEAE:** any AE that increased in severity or that was newly developed after the end of the Treatment-emergent Period of the Cumulative Study Period.

AEs with missing or partial start dates, if there is no clear evidence that the AEs started before or after study treatment, then the AEs will be classified as TEAEs.

All TEAE summaries will be described, using number and percentages of subjects, as well as number of events per 100 patient-years (number of events adjusted for the total duration of exposure) for the Cumulative Study Period. An overview of the TEAE profile will be provided, including total number of TEAEs, with number and percentage of subjects as well as number of events per 100 patient-years for the following categories: (1) all TEAEs; (2) Grade 3/4 TEAEs; (3) TEAEs by relationship; (4) TEAEs by maximum severity; (5) TEAEs leading to treatment interruption; (6) TEAEs leading to treatment discontinuation; (7) serious TEAEs; (8) related serious TEAEs; and (9) TEAEs leading to death.

AE summary tables will be presented for TEAEs only and will include the following:

- All TEAEs
- Grade 3/4 TEAEs
- TEAEs by relationship
- TEAEs by maximal severity
- TEAEs leading to treatment interruption
- TEAEs leading to treatment discontinuation
- Serious TEAEs
- Related serious TEAEs
- TEAEs leading to death
- Frequently reported TEAEs

Summaries will be presented by MedDRA system organ class (SOC) and preferred term (PT) using frequency counts and percentages and number of events per 100 patient-years (i.e., number and percentage of subjects with an event as well as exposure-adjusted number of events). When summarizing the number and percentage of subjects with an event, subjects with multiple occurrences of the same AE or a continuing AE will be counted once, only the maximum severity level will be presented in the severity summaries, and the worst/highest relationship

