### **8.2 Safety Set**

**116 Safety Set:** The 116 Safety Set will include all subjects dosed in Study 115B who are exposed to any amount of study drug in the Study 116 Treatment Cohort.

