### 10.5.1 Adverse Events

For analysis purposes, AEs will be classified as TEAEs, or post-treatment AEs.

- **TEAE:** any AE that increased in severity or that was newly developed during the Treatment-emergent Period of the Current Study Period.
- **Post-treatment AE:** any AE that increased in severity or that was newly developed after the end of the Treatment-emergent Period of the Current Study Period.

For AEs with missing or partial start dates, if there is no clear evidence that the AEs started before or after study treatment, then the AEs will be classified as TEAEs. Details for imputing missing or partial start dates of AEs are described in [Appendix E](#).

TEAE summaries will be presented using number and percentages of subjects for the Current Study Period based on 116 Safety Set.

An overview of the TEAE profile will be provided, including total number of TEAEs, with number and percentage of subjects for the following categories: 1) all TEAEs; 2) Grade 3/4 TEAEs; 3) TEAEs by relationship; 4) TEAEs by maximum severity; 5) TEAEs leading to treatment interruption; 6) TEAEs leading to treatment discontinuation; 7) serious TEAEs; 8) serious TEAEs related to study drug; and 9) TEAEs leading to death.

AE summary tables will be presented for TEAEs only and will include the following:

- All TEAEs
- Grades 3/4 TEAEs
- TEAEs by relationship to study drug
- TEAEs by maximal severity
- TEAEs leading to treatment interruption
- TEAEs leading to treatment discontinuation
- Serious TEAEs
- Serious TEAEs related to study drug
- TEAEs leading to death
- Frequently reported TEAEs ( $\geq 5\%$  at the preferred term level for the overall column)

Summaries will be presented by MedDRA SOC and PT using frequency counts and percentages (i.e., number and percentage of subjects). When summarizing the number and percentage of subjects with an event, subjects with multiple occurrences of the same AE or a continuing AE will be counted once, only the maximum severity level will be presented in the severity summaries, and the worst/highest relationship level in the relationship summaries.

In addition, listings containing individual subject data for all TEAEs leading to treatment interruption, TEAEs leading to treatment discontinuation, deaths, and SAEs will be provided separately. All AEs, including pre- and post-treatment AEs, will be presented in individual subject data listings.

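### The SAP drops the protocol's cumulative safety analysis: the population shrinks to Study 116 rollover subjects, the period to Study 116 only, and the event rates per 100 patient-years disappear

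*SAP*

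**What the plan says.** **Protocol.** The synopsis states: "The safety analysis for the Cumulative Study Period will be based on the Safety Set". Section 12.2 defines that set: "The Safety Set will include all subjects who received at least 1 dose of study drug in Study 115B". The matching treatment-emergent window for subjects who did not enter Study 116 is "the period on or after the first dose of study drug in the previous study to 14 days (inclusive) after the last dose" in 115B, or their last date in that study if earlier; for the others it runs on through Study 116. Section 12.3.4.1 asks for numbers and percentages of subjects and for "number of events per 100 patient-years (number of events adjusted for the total duration of exposure) for the Cumulative Study Period", in the overview and by system organ class (SOC) and preferred term (PT). Section 12.3.2.4 measures exposure as last dose date minus "first dose date of the Cumulative Study Period + 1 day, regardless of any dose interruptions".

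**SAP.** Section 8.2 defines only the 116 Safety Set: "all subjects dosed in Study 115B who are exposed to any amount of study drug in the Study 116 Treatment Cohort". Section 9.2 keeps the Cumulative Study Period but defines no treatment-emergent period for it. Section 10.5 then says: "The safety summaries described in the sections below will be performed for the Treatment Cohort based on the Current Study Period only". Section 10.5.1 redefines treatment-emergent adverse events (TEAEs) on the Study 116 window and drops the rates: "TEAE summaries will be presented using number and percentages of subjects for the Current Study Period based on 116 Safety Set". Among the visible analyses, only pulmonary exacerbations and CF-related hospitalizations (Section 10.3.2.6) remain cumulative.

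**The concern.** The primary objective is long-term safety. Protocol Section 9.3.2 justifies the dosing duration by the combined 115B and 116 treatment, put at up to about 2.5 years. The SAP describes only the Study 116 part, in a selected group.

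The selection is not neutral. Exclusion criterion 1 bars from the Treatment Cohort anyone who prematurely discontinued drug in 115B. Criteria 3, 5 and 6 can also remove subjects with drug intolerance, unexplained liver test abnormalities or QTc values of concern. The SAP tabulates liver test and QTc thresholds and treats elevated transaminases as an event of special interest, so its tables leave out subjects screened out for signals they are meant to describe. Those who joined the Observational Cohort appear only in listings, which for safety means Study 116 SAEs. The rollover subjects' own first 24 weeks on drug are also uncounted.

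Losing the rates matters separately. SAP Section 10.2.1 anticipates subjects leaving before Week 96 for commercial drug, and crude percentages fall as follow-up shortens.

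**Working it through.** **Documents side by side**

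| Element | Protocol | SAP |
|---|---|---|
| Population | All dosed in 115B | Dosed in 115B and again in the 116 Treatment Cohort |
| Period | First 115B dose to end of 116 | First 116 dose to end of 116 |
| TEAE measure | n (%) and events per 100 patient-years | n (%) only |

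**Inputs from the documents.** About 56 potentially eligible, 10% dropout in 115B and 50 expected (protocol 12.1); 24 weeks of treatment in 115B (9.3.1); 96 weeks in 116 (9.1.2.1); a planned 2-week washout (12.2). The plan's own figure reproduces: 56 × 0.90 = 50.4, stated as 50.

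**Assumptions.** The 56 stand in for the number dosed in 115B. All 50 enter the Treatment Cohort and complete 96 weeks. The other 6 had 4 to 24 weeks on drug. Patient-years (PY) = weeks × 7/365.25.

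**Subjects omitted.** 6/56 = 10.7%.

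**On-drug exposure**
- SAP: 50 × 96 = 4,800 weeks = 92.0 PY.
- Cumulative: 50 × 120 + 6 × (4 to 24) = 6,024 to 6,144 weeks = 115.4 to 117.7 PY.
- Omitted: 1 − 4,800/6,024 = 20.3%, to 1 − 4,800/6,144 = 21.9%.

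**Protocol exposure definition** (first to last dose, so the 2-week washout counts; no further gap assumed)
- 50 × 122 + 6 × (4 to 24) = 6,124 to 6,244 weeks = 117.4 to 119.7 PY.
- Omitted: 21.6% to 23.1%.

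**Other enrolment and duration assumptions (on-drug exposure)**
- 45 in the Treatment Cohort, 11 others: 82.8 against 104.3 to 108.6 PY; 20.6% to 23.7% omitted.
- 40 in the Treatment Cohort, 16 others: 73.6 against 93.2 to 99.4 PY; 21.1% to 25.9% omitted.
- 50 subjects averaging only 48 weeks in 116, and the other 6 having 0 to 24 weeks: 2,400 of 3,600 to 3,744 weeks are kept, so 33.3% to 35.9% is omitted.

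**What selection could hide (illustration; event counts assumed).** Suppose 1 to 6 subjects stopped in 115B for a given event and none has it in 116. The SAP table shows 0/50 (Clopper-Pearson 95% CI 0 to 7.1%). The protocol table shows between 1/56 (1.8%, CI 0.0 to 9.6%) and 6/56 (10.7%, CI 4.0 to 21.9%).

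**Effect of early exit on crude percentages (illustration; hazards and exit shares assumed).** If a fraction f leaves at Week 48 (0.920 years) and the rest reach Week 96 (1.840 years), with constant hazard h:

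incidence = (1 − f)(1 − exp(−1.840h)) + f(1 − exp(−0.920h))

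| h per year | f = 0 | f = 0.25 | f = 0.50 | f = 0.75 |
|---|---|---|---|---|
| 0.1 | 16.8% | 14.8% | 12.8% | 10.8% |
| 0.5 | 60.1% | 54.3% | 48.5% | 42.7% |

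The rate per 100 PY does not change across a row.

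**Year unit.** SAP Section 10.2.4 counts 48 weeks as one subject-year. Then 4,800/48 = 100 subject-years for what is 92.0 calendar years, and a rate on that denominator is understated by 1 − 92.0/100 = 8.0%.

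**The case against.** The best defence is that less is lost than appears.

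- Study 115 has its own safety objective, so the 115B events will be reported.
- The SAP's FAS is essentially the 115B-dosed population, and exacerbations and CF-related hospitalizations are still analysed on it from first dose, so part of serious morbidity stays integrated.
- Laboratory, ECG, vital-sign, oximetry and spirometry changes still use the 115B baseline.
- The SAP reports the total number of TEAEs and total subject-years, so a crude overall Study 116 rate can be derived, and counts by PT could be made by hand from the listings.
- Some selection is inherent in a rollover study. The protocol itself uses the 116 Safety Set for disposition, demographics and prior medication.
- SAP Section 3 is redacted and may explain the change.

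All of this is accurate, and it limits the finding. None of it brings back the omitted subjects or the 115B TEAEs in a combined table, and no planned table gives rates by SOC or PT. Protocol Section 12.2 lets the SAP define other periods for targeted analyses, which does not extend to replacing the main one. An explanation in the redacted section would document the change without restoring the analysis.

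Two criticisms of the numbers are fair. The 4-week minimum for the 6 non-rollover subjects is an assumption; 0 weeks moves the lower bound only from 20.3% to 20.0%. The protocol's exposure definition also counts washout and any rollover gap, when Study 116 events may not yet be collected, which could dilute a rate. The figures above include no gap beyond the washout, so that effect is not quantified here.

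**Conclusion.** The concern holds. Population, period and measure of the primary safety analysis all differ between the two documents, and no visible SAP text reinstates the protocol's version. On the planned numbers about one subject in ten and about a fifth of on-drug exposure leave the safety tables. The exposure share is 20.3% to 21.9% in the main case, up to 25.9% with a smaller Treatment Cohort, and 33.3% to 35.9% if mean Study 116 exposure is only 48 weeks. These figures rest on 56 as a proxy for the number dosed and on assumed 115B exposure in those who did not roll over. The textual discrepancy rests on neither. It cannot be said that the change is unexplained, because part of the SAP is redacted. Since it concerns the prespecified analysis of the primary objective, it must be fixed.

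**What to change.** 1. Restore the Safety Set in SAP Section 8.2 and the treatment-emergent period of the Cumulative Study Period in Section 9.2.
2. Produce the protocol's TEAE overview, SOC/PT, treatment-discontinuation, SAE and laboratory-threshold tables for the Cumulative Study Period on the Safety Set, beside the Current Study Period tables on the 116 Safety Set. Give n (%) and events per 100 patient-years in both. Rates for the Current Study Period go beyond the protocol but make the two sets comparable.
3. Compute patient-years by the protocol's exposure definition on a stated calendar-year basis, not 48 weeks to the year.
4. If washout and rollover-gap days are left out, label that a sensitivity analysis and leave out the events on those days too.

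Cumulative tables for events of special interest are optional, because the protocol defines none.

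The cost is SAP wording, programming and a second set of safety tables. No new data are needed: the SAP already combines 115B and 116 data for exacerbations and hospitalizations.
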